Suprainguinal Fascia Iliaca (SIFI) Block Improves Analgesia Following Total Hip Arthroplasty

Document Date: December 11, 2019

NCT02933671

1. Protocol Title:

Suprainguinal Fascia Iliaca (SIFI) Block Improves Analgesia Following Total Hip Arthroplasty.

2. Purpose of the Study:

The goal of this prospective randomized double-blind study is to determine if an ultrasound guided suprainguinal fascia iliaca (SIFI) technique is efficacious as an analgesic for total hip arthroplasty. Efficacy will be determined by analyzing post-intervention pain scores (NRS 11), opioid consumption, and functional status including ambulation and dynamometry for quadriceps function. English speaking ASA 1-3 patients ages 18-75 years old undergoing primary total hip arthroplasty will be assessed post-operatively after a general anesthetic. Once pain scores are $>5/10$, patients will be blocked with either 0.2% ropivacaine or saline, and numerical pain scores and opioid consumption will be evaluated over the following 24 hours. Data will be analyzed on an intent to treat basis using a two-sided t-test (parametric) or Mann-Whitney-Wilcoxon (non-parametric) with a p-value of 0.05 as significant. Patients will assume standard risk associated with nerve blocks, including theoretical risk of nerve damage and local anesthetic systemic toxicity.

3. Background & Significance:

Several regional anesthesia techniques have been implemented to decrease postoperative pain following total hip arthroplasty (THA), with varying success^{1,2}. Of these, the fascia iliaca block is commonly utilized nerve block for hip surgery. This block anesthetizes the lateral femoral cutaneous nerve (LFCN), but has a reported 10-37% failure rate³⁻⁵. To reduce failure, the femoral nerve and the LFCN have been blocked individually utilizing ultrasound guidance. The LFCN, if blocked individually, has traditionally been approached below the inguinal ligament³⁻⁸ and has been shown to be useful in patients with chronic pain. In chronic pain, desired sensory block of the LFCN while avoiding motor block is important, leading to deposition of local anesthetic distal to the inguinal ligament.

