Patients will be randomized into either SIFI block or sham group with an online randomization program by the study PI ([name]) prior to any patient enrollment. Patients will be given a number (1-40), and the randomized numbers will be given to key study personnel member that will be unblinded. The intervention drug, either 30mL 0.2% ropivacaine or sham block, consisting of 30mL saline, will be drawn up by this key personnel member of the study team who is unblinded and will not be involved in the SIFI block or post-operative analysis. This person will supply the regional anesthesiologist with the intervention, however, both the regional anesthesiologist performing the block and the patient will be blind as to the contents of the syringe.

At the completion of the intervention, verbally reported pain scores (NRS 11) and opioid consumption (IV morphine equivalents) will be measured by a blinded observer starting at time zero and monitored every 10 minutes for 1 hour (+/- 5 minutes). Verbal pain scores will then be recorded each hour for first 4 hours, 6 hours and 24 hours (+/- 10 minutes). Patients will have post-operative orders for supplementary pain control that

include 25mcg IV fentanyl for pain scores 5-7 and 50mcg IV fentanyl for pain scores 8-10.

Subjects' verbal pain scores and opioid consumption will be recorded hourly for the first four hours, at 6 hours, and at 24 hours. Dynamometry will be utilized 2 hours post intervention on POD0 to determine the extent of quadriceps weakness achieved by SIFI injection as compared to unblocked leg. Ambulation distance in feet will be measured POD0 and POD1 by physical therapy. These results will be recorded as will hospital length of stay.

5. Selection of Subjects:

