Benefits include contributing to general knowledge base to improve future patient care. This includes potential confirmation of analgesic benefit, decreased pain scores, and improved patient satisfaction. Conversely, this study may show no benefit of the block, thereby invalidating the technique.

11. Costs to the Subject:

Subjects will not incur any additional costs to participate in the study. A MaestroCare build will be created to ensure that any subjects are not charged for researched related procedures, equipment, or medications.

12. Data Analysis & Statistical Considerations:

The primary hypothesis, that there is a difference in numeric pain score at 4 hours postoperatively between the intervention groups, will be assessed with a two-sided 2 group t-test or Mann-Whitney-Wilcoxon test as appropriate. We will perform a secondary repeated measures ANOVA or non-parametric Friedman test to assess difference in numeric pain score over the full 24-hour period. If there is evidence of a difference in numeric pain score during the 24-hour period, we will perform post-hoc pair-wise multiple comparison corrected tests to identify the time-points where the intervention groups differ on pain score. Additional secondary analyses will assess differences in cumulative opioid consumption in IV morphine equivalents and motor strength for both tibial and common peroneal nerves with parametric or non-parametric tests as appropriate. Statisticians employed by the Department of Anesthesiology will conduct these analyses.

A total of 40 participants will be enrolled in the study, randomized equally between study (n=20) and placebo (n=20) groups based on sample size calculation for a non-parametric Mann-Whitney Test with $\alpha=0.05$, $\beta=0.8$, difference in means=2, and effect size of 1.0. The sample size required for a non-parametric test will provide greater than 80% power if the data meet requirements for a parametric t-test.

13. Data & Safety Monitoring:

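### The secondary 24-hour pain analysis has no rule for missed scores; its named methods by default keep only complete patients, and the Friedman option does not compare block with sham

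*Combined protocol and SAP*

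**What the plan says.** Section 12 (Data Analysis & Statistical Considerations) makes the pain score at 4 hours the primary comparison, under the hypothesis "that there is a difference in numeric pain score at 4 hours postoperatively between the intervention groups". For the whole 24-hour course it adds: "We will perform a secondary repeated measures ANOVA or non-parametric Friedman test to assess difference in numeric pain score". If that analysis shows a difference, time-point comparisons with multiplicity correction follow, so it acts as their gate.

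Section 4 (Design & Procedures) sets the schedule. Scores are taken "starting at time zero and monitored every 10 minutes for 1 hour (+/- 5 minutes", and then: "Verbal pain scores will then be recorded each hour for first 4 hours, 6 hours and 24 hours (+/- 10 minutes".

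Section 2 (Purpose of the Study) gives the analysis basis: "Data will be analyzed on an intent to treat basis using a two-sided t-test (parametric) or Mann-Whitney-Wilcoxon (non-parametric".

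No section says how a missed score is handled, whether incomplete patients are dropped, how the ANOVA would be fitted, which of the scheduled scores enter it, or what rate of missing scores is expected.

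**The concern.** A classical repeated measures ANOVA and a standard Friedman test both need a full row of scores for each patient. One missed score removes that patient's other scores from the analysis. With 20 patients per arm, a few removals matter.

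The removals may also be selective. Section 3 onward describes sedation during surgery and fentanyl given by pain score afterwards, so a patient too drowsy to answer may be one whose earlier pain was high. Length of stay is recorded as an outcome and can vary, and a comfortable patient who goes home before 24 hours may have no last score. Either route could relate to pain, and possibly to arm, so a complete-case comparison could be biased as well as less precise.

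The second problem does not depend on missing data. The Friedman test asks whether scores differ between times within patients. If it is the method used, the gate to the between-group time-point comparisons is opened by a test that contains no group comparison.

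**Working it through.** **Inputs**
- Score times (Section 4): 0, 10, 20, 30, 40, 50 and 60 min give 7. The later schedule is 1, 2, 3, 4, 6 and 24 h; 1 h is the 60-min score, so it adds 5. Total k = 12. If only the 1, 2, 3, 4, 6 and 24 h scores are used, k = 6.
- Patients (Section 12): 40, with 20 per arm.
- Miss rate per score, m: not in the documents. Assumed 1% to 5%.
- Correlation of misses within a patient, rho: not in the documents. Assumed 0 (independent) up to 0.8.

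**Step 1: the plan's own figure.** The inputs are two-sided alpha 0.05, power 80% (Section 12 writes beta = 0.8, which only makes sense as power), a difference of 2 and an effect size of 1.0, so SD = 2 / 1.0 = 2. The exact two-sample t-test needs 16.71 per arm. Dividing by 0.864, the lower bound for the relative efficiency of the Mann-Whitney test, gives 19.35, so 20 per arm and N = 40, as stated. The t-test with 20 per arm has 86.9% power, consistent with the plan's claim of more than 80%. N therefore rests on a two-group comparison of the kind planned at 4 hours, not on the 24-hour analysis.

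**Step 2: complete-case loss, independent misses.** Share lost = 1 - (1 - m)^k.

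| m per score | k = 12: share lost | of 40 | k = 6: share lost | of 40 |
|---|---|---|---|---|
| 1% | 1 - 0.886 = 11.4% | 4.5 | 5.9% | 2.3 |
| 2% | 1 - 0.785 = 21.5% | 8.6 | 11.4% | 4.6 |
| 3% | 1 - 0.694 = 30.6% | 12.2 | 16.7% | 6.7 |
| 5% | 1 - 0.540 = 46.0% | 18.4 | 26.5% | 10.6 |

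**Step 3: the same rates with misses clustered in patients, k = 12.** Beta-binomial model: s = 1/rho - 1, a = m s, b = (1 - m) s; share lost = 1 - B(a, b + 12) / B(a, b).

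| rho | m = 2% | m = 5% |
|---|---|---|
| 0.1 | 15% | 33% |
| 0.3 | 9% | 21% |
| 0.5 | 6% | 15% |
| 0.8 | 3% | 8% |

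Moderate clustering (rho 0.3 to 0.5) gives about 6% to 21%.

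**Step 4: retention under a mixed model.** A likelihood-based mixed model leaves out a patient only if every score is missing. In 5,000 simulated trials of 40 patients with 12 scores and independent misses, complete cases averaged 31.5 at m = 2% (5th to 95th percentile 27 to 36) and 21.6 at m = 5% (17 to 27). Patients with at least one score averaged 40.0 at both rates.

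**Step 5: what the Friedman test compares.** It ranks the scores within each patient and compares rank sums across times. Subtract 2 points, the planned difference, from every score in one arm (ignoring the floor at 0). All within-patient ranks, and so the test statistic, stay the same. A constant block effect is invisible to it, while any change over time shared by both arms can make it significant.

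**The case against.** The strongest reply is that the plan never says incomplete patients are dropped. Deletion is the default of the classical fit. The name repeated measures ANOVA is also used loosely for mixed models or for analyses with imputed scores, and those keep the patients. This stands: the documents support an omission, not a stated deletion rule. The looser reading does not rescue the Friedman option.

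A reader might infer that the plan contradicts its intent-to-treat promise. The documents do not go that far. The sentence in Section 2 is tied to the t-test and the Mann-Whitney-Wilcoxon test, and intent to treat mainly fixes the arm in which a patient is counted. Its subject is the data in general, however, so a complete-case default remains a poor fit.

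A reader might also infer that a fifth to almost half of the patients will be lost. That holds only for 12 scores, each missed independently at 2% to 5%. The documents give neither the rate nor the independence. Drowsiness and early discharge would tend to concentrate misses in a few patients, which lowers the loss. A blinded observer collects the scores, nothing says that a score outside its window is discarded, and the 10-minute scores may not all enter the model.

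Finally, a mixed model does not by itself deliver full intent to treat. Randomisation numbers are fixed before enrolment, and the block is given only after the pain threshold is reached, so a randomised patient who never reaches it has no post-block score. The model also needs scores to be missing at random and treats a bounded 0 to 10 score as roughly normal. These limits stand and belong in the fix.

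**Conclusion.** The point holds as a gap in a secondary analysis. The 24-hour analysis has no missing-score rule, both named methods use complete patients only in their standard form, and the Friedman option does not test block against sham. The first two follow from the text and the usual form of the methods; the third needs no assumption about missing data.

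The size of the patient loss is conditional. For 12 scores with independent misses it is 11% at 1% per score, 21.5% at 2% and 46% at 5%. At 2% to 5% it is about 6% to 21% with moderate clustering, and 11% to 27% with independent misses on six scores. No single figure can be called the expected loss.

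It would be wrong to conclude that the main result is at risk from this. The primary test needs only the 4-hour score, a patient dropped from the 24-hour analysis can still contribute that score, and N = 40 is reproduced without reference to repeated measures. What is exposed is the 24-hour comparison and the time-point tests that depend on it. The sponsor should correct it, but it is not critical to the trial.

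**What to change.** In Section 12, replace the sentence naming the repeated measures ANOVA or Friedman test with the following specification:

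- A linear mixed model on all available post-block pain scores, with arm, categorical time and arm-by-time as fixed effects, within-patient correlation, and Kenward-Roger degrees of freedom. Name the score times that enter.
- Include every randomised patient with at least one post-block score, in the assigned arm. Account separately, by arm, for randomised patients with none.
- Use the test of arm and arm-by-time as the gate to the corrected time-point comparisons.
- Report the number of scores obtained by arm and time, so that readers can judge the pattern of missing data.
- State that the model assumes scores are missing at random, and keep Mann-Whitney tests by time point as a non-parametric sensitivity check, because the score is bounded.

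The cost is SAP wording and standard software. No new data, visits or patients are needed. The price is reliance on the missing-at-random and approximate normality assumptions, which is why both should be stated and the sensitivity check kept.

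### The secondary 24-hour pain analysis names no tested effect, time points or sphericity correction; on the fuller schedule its unweighted group effect is mostly a first-hour effect (minor)

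*Combined protocol and SAP*

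**What the plan says.** Section 12 makes the pain score at 4 hours the primary comparison. It then adds a "secondary repeated measures ANOVA or non-parametric Friedman test to assess difference in numeric pain score over the full 24-hour period". Pairwise tests corrected for multiple comparisons, meant to locate the times at which the groups differ, follow on one condition: "If there is evidence of a difference in numeric pain score during the 24-hour period". Section 12 does not say whether the group effect or the group-by-time effect supplies that evidence. It lists no time points and gives no covariance structure, sphericity correction or handling of missing scores.

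Section 4 describes the schedule twice. The fuller description has scores "starting at time zero and monitored every 10 minutes for 1 hour (+/- 5 minutes"), counted from completion of the intervention. It continues: "Verbal pain scores will then be recorded each hour for first 4 hours, 6 hours and 24 hours (+/- 10 minutes"). The next paragraph of Section 4 says that "verbal pain scores and opioid consumption will be recorded hourly for the first four hours, at 6 hours, and at 24 hours", with no mention of the 10-minute readings.

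**The concern.** Three features of the fuller schedule matter.

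- **Weighting.** The group effect in a repeated-measures ANOVA compares plain patient means. Every reading counts equally, whether it stands for 10 minutes or for many hours. With readings packed into the first hour, a result presented as covering 24 hours could rest mainly on that hour.
- **Time zero.** This reading is taken as the block is completed, so it can carry little treatment effect. Nothing removes it from the outcomes.
- **Sphericity.** Scores taken 10 minutes apart are likely to be more alike than scores 18 hours apart. If correlation decays with time, sphericity fails and an uncorrected group-by-time F test rejects too often. Under Section 12 that test may decide whether time-point testing begins.

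At stake is how a secondary result is read. A short benefit and a lasting one could give similar 24-hour differences, and an interaction p-value could look stronger than it is.

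**Working it through.** **1. The plan's own figure.** The only design figure is 40 patients (20 per arm), and it belongs to the 4-hour comparison. A difference of 2 with effect size 1.0 implies SD = 2/1.0 = 2. The normal approximation gives 2 × (1.96 + 0.84)² / 1.0² = 15.7, so 16 per arm; the noncentral t gives 16.715. Dividing by 0.864, the minimum efficiency of the Mann-Whitney test, gives 16.715/0.864 = 19.35, so 20 per arm. The figure is reproduced. No figure is given for the repeated-measures analysis.

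**2. Time points.** Fuller schedule: 0, 10, 20, 30, 40, 50 and 60 minutes, then 2, 3, 4, 6 and 24 hours. That is 12 distinct times, 7 of them at or before 60 minutes. Shorter restatement: 1, 2, 3, 4, 6 and 24 hours, so 1 of 6.

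**3. Weights on the fuller schedule.** Unweighted, the first hour carries 7/12 = 58.3%. By the trapezoid rule, each score has weight (next time − previous time)/(2 × 24), with half-intervals at the ends:

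| Score | Weight |
|---|---|
| 0 min | 0.0035 |
| 10 to 50 min, each | 0.0069 |
| 60 min | 0.0243 |
| 2 h and 3 h, each | 0.0417 |
| 4 h | 0.0625 |
| 6 h | 0.4167 |
| 24 h | 0.3750 |

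The scores up to 60 minutes sum to (1 + 0.5)/24 = 6.25%. The interval from 6 to 24 hours is 18/24 = 75% of the period and has no reading inside it.

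**4. Illustrative benefits of 2 points.**

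| Benefit present at | Unweighted mean difference | Time-weighted mean difference |
|---|---|---|
| 10 to 60 min only | 2 × 6/12 = 1.00 | 2 × (0.0625 − 0.0035) = 0.12 |
| 2 to 24 h only | 2 × 5/12 = 0.83 | 2 × (1 − 0.0625) = 1.88 |

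The unweighted mean ranks the brief benefit above the lasting one.

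**5. Error rate.** Null trials were simulated with 20 patients per arm, 12 times and 20,000 runs per row. The covariance is assumed, because the documents give none: a patient intercept, a serial part exp(−lag/τ) and independent noise, in the variance shares shown. Epsilon is 1 when sphericity holds. Entries are rejection percentages at a nominal 5% for τ = 1, 2 and 4 hours.

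| Intercept / serial / noise | Epsilon | Group-by-time, uncorrected |
|---|---|---|
| 0 / 1 / 0 | 0.52, 0.41, 0.34 | 9.8, 10.8, 12.8 |
| 0.3 / 0.5 / 0.2 | 0.72, 0.66, 0.65 | 7.5, 7.5, 7.8 |
| 0.5 / 0.3 / 0.2 | 0.80, 0.76, 0.76 | 6.7, 6.4, 7.0 |
| 0.4 / 0.2 / 0.4 | 0.94, 0.93, 0.94 | 5.5, 5.5, 5.7 |

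Across these rows the group main effect rejects in 4.8 to 5.2%. The group-by-time test rejects in 3.3 to 4.8% with the Greenhouse-Geisser correction and 4.7 to 5.4% with Huynh-Feldt. Under compound symmetry the uncorrected test is at 4.8%.

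**6. Six scores only.** With the same kind of decaying correlation and no noise, the uncorrected group-by-time test rejects in about 6 to 8%.

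**7. Time-point claims.** Section 12 does not name the multiplicity correction, so Bonferroni is assumed. A false claim at any time point then arises in about 1 to 3% of null trials, whether the gate is the interaction alone or either effect.

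**8. Friedman alternative.** The test ranks scores within each patient, so adding a constant to every score in one arm changes no rank. In 4,000 simulated trials per setting, group shifts of 0, 2 and 4 points all left its rejection rate at about 6%. It tests change over time, not a difference between groups.

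**The case against.** The strongest reply is that this is a gap in wording with limited consequences.

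- A reader might infer that the whole analysis has an inflated error rate. The documents do not support that. The group main effect is a test on patient means and needs no sphericity. Section 12 does not name the interaction as the deciding test.
- A reader might infer that the plan assumes sphericity. It is silent, and the usual corrections are options within repeated-measures ANOVA. Silence does leave an uncorrected test permissible.
- A reader might infer that false time-point claims exceed 5%. They do not, because those tests carry their own correction and a gate can only remove rejections. The same tests would also help to show that a benefit was confined to the first hour.
- Uneven spacing does not by itself break sphericity; decaying correlation does. The 10 to 13% figure needs almost noise-free scores, and the true covariance is unknown.
- The count of 7 of 12 depends on the fuller schedule, and Section 4 also supports six scores.
- A reader might infer that a patient with one missing score is dropped. No such rule is stated, and Section 2 plans analysis by intention to treat.
- A time-weighted mean has its own weakness. Without time zero, the 6-hour and 24-hour scores carry (10 + 9)/23.83 = 80% of the weight.

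All of these stand, and they limit the point to a minor one. They do not remove the weighting problem on the fuller schedule, which is arithmetic and needs no covariance assumption. Nor do they supply the missing tested effect and time points.

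**Conclusion.** The point holds as a minor one, confined to a secondary analysis. If all 12 scores enter, the unweighted group effect puts 58% of its weight on the first hour, against 6.25% by time, and it includes a reading taken as the block is completed. Calling that average a 24-hour effect would mislead.

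Inflation is confined to an uncorrected group-by-time test. It is about 10 to 13% under assumed correlation decaying over 1 to 4 hours without noise, and about 6 to 8% with 20 to 40% noise or with six scores. These rates rest on covariances that the documents do not give. The weighting result rests only on the fuller schedule and on equal weighting of scores.

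It would go too far to say that the analysis as a whole fails its 5% level or says nothing about later hours. The 6-hour and 24-hour scores do enter the interaction and the time-point tests. The 4-hour primary comparison is untouched.

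**What to change.** Amend Section 12 as follows.

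- Replace the ANOVA or Friedman test with a linear mixed model of the post-baseline scores, using all available data. Include treatment, time as a category, treatment-by-time and the pre-block trigger score as covariate. Use a covariance that lets correlation decay with time (for example spatial power plus a patient intercept) and small-sample degrees of freedom such as Kenward-Roger.
- Remove time zero from the outcomes. This alone does not cure the weighting, since 6/11 = 55% of the remaining scores still fall in the first hour.
- List the time points, settling which Section 4 description applies, and name the effect that counts as evidence of a difference.
- If ANOVA is kept, require the Greenhouse-Geisser correction.
- Do not describe the unweighted average as a 24-hour effect. Report a time-weighted mean beside it as a descriptive summary, noting that there is no reading between 6 and 24 hours.

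The cost is SAP wording and slightly more analysis work, with no new data collection. The interaction test becomes slightly less liberal, so it will reach significance a little less often. Making the time-weighted mean the sole 24-hour summary is not advised, because two scores would dominate it.

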Anterior approaches for total hip arthroplasty have led to careful cadaveric examination of the course of the LFCN⁹⁻¹¹ following reports of LFCN damage caused by the anterior approach^{8,9}. The LFCN has an unreliable course with variable branching below the inguinal ligament. The branching is variable such that one or more branches may course above, through, or below the inguinal ligament. The branches may cross *sartorius* laterally anywhere from 0-9 cm below the inguinal crease⁹⁻¹¹. In contrast, the LFCN has a reliable course above the inguinal ligament and conserved course superficial to *iliacus* muscle and immediately below the fascia iliaca in the pelvis⁸.

Swenson, *et al.*¹², described injection of local anesthetic under the fascia iliaca at the level of the inguinal ligament with subsequent distal compression to advance the local anesthetic in a retrocaudal direction with MRI confirmation of distribution using dye. Sensory deficit in the distribution of the LFCN was demonstrated in all patients although local anesthetic was up to 2.2 cm laterally from the ASIS in 40% of their subjects. This technique, however, causes a significant motor block since local anesthetic is injected near the femoral nerve.

Hebbard, *et al.*¹³, described an infrainguinal approach for suprainguinal needle placement in cadavers and demonstrated dye surrounding LFCN in the pelvis by advancing the needle in a cephalad direction underneath the inguinal ligament¹³. Despite the potential advantages of the suprainguinal needle placement, the long needle entry path and difficulty imaging the correct fascial plane, particularly in obese patients, can

make this approach challenging. As such, this approach has not been widely studied in the several years since its description.

Similarly, Kumar, *et al.*¹⁴, described a modified suprainguinal approach using a landmark based technique during which the needle was placed 1 cm above the inguinal ligament and 1/3 of the distance medially from the ASIS to the pubic tubercle. With this technique, decreased VAS pain scores were seen, as was less morphine consumption and less post-operative nausea and vomiting than patients receiving traditional infrainguinal fascia iliaca blocks, showing a benefit for suprainguinal injection.

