Our recent case series comprised of 5 patients described the novel ultrasound guided out-of-plane suprainguinal fascia iliaca (SIFI) plane block¹⁵. The approach described requires new probe positioning and new sonographic landmarks for combined LFCN and femoral nerve analgesic block. Pain scores were slightly lower in the block group, however, opioid consumption was decreased. Gross motor function was preserved despite local anesthetic tracking down to femoral nerve, however no qualitative measures were taken. Overall, the ultrasound guided SIFI approach to anesthetizing the LFCN showed promise, but has not been adequately evaluated for efficacy in a prospective study.

4. Design & Procedures:

Preoperatively, patients will be given standard of care premedications: 975mg acetaminophen and 300mg gabapentin by mouth prior to surgery. These medications may be altered or not given depending on patient comorbidities or other extenuating factors such as allergy/intolerance. Furthermore, a spinal anesthetic will be placed in the preoperative area.

Patients will be taken to the operating room and sedated using IV propofol to a bispectral index (BIS) of 60-80, indicating adequate sedation. Once sedated, patients will be given a 0.5mg/kg ketamine bolus (based on ideal body weight) and 10mg dexamethasone will be given prior to incision. The orthopedic surgery attending will determine the degree of preoperative knee extension prior to the procedure and inform the anesthesia team. At conclusion of the case sedation will be stopped and patient will be taken to the post-operative care unit (PACU).

Post-operatively study interventions will begin. Patients will be assessed from arrival in PACU to determine their level of pain as well as nausea/vomiting. Once the patient reported pain score in the recovery area is $\geq 5/10$ on a 0-10 numerical pain scale study personnel will initiate intervention. Patients will be given a one time IV bolus of 15mg ketorolac.

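### Section 12 plans to test tibial and common peroneal motor strength, which is never scheduled, and omits the quadriceps dynamometry and ambulation that are

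*Combined protocol and SAP*

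**What the plan says.** Section 12 sets out the primary test of pain score at 4 hours and a repeated-measures analysis over 24 hours. It then adds two secondary analyses in one sentence: cumulative opioid consumption, and "motor strength for both tibial and common peroneal nerves with parametric or non-parametric tests as appropriate".

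Section 2 says efficacy will be judged on pain scores, opioid consumption and "functional status including ambulation and dynamometry for quadriceps function". It also gives a general rule for all data: intent to treat, with a two-sided t-test or Mann-Whitney-Wilcoxon test at 0.05.

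Section 4 schedules the measurements. On strength it says "Dynamometry will be utilized 2 hours post intervention on POD0", with the aim of determining "the extent of quadriceps weakness achieved by SIFI injection as compared to unblocked leg". On function it says "Ambulation distance in feet will be measured POD0 and POD1 by physical therapy". Hospital length of stay is also recorded. Section 9 only refers back to Section 4, so there is no second schedule.

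Section 3 gives the motor background. It says of an earlier technique, with injection at the inguinal ligament, that it "causes a significant motor block since local anesthetic is injected near the femoral nerve". Of the team's own case series it reports: "Gross motor function was preserved despite local anesthetic tracking down to femoral nerve, however no qualitative measures were taken".

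**The concern.** The outcome to be analysed and the outcome to be measured are different. Section 12 commits the trial to a test on two nerves for which the protocol plans no assessment, and is silent on the strength measure that the protocol does plan.

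An analyst following Section 12 literally would have to report a prespecified analysis as not done. An analyst who used dynamometry instead would be substituting an endpoint by inference, and a reader comparing the report with the plan would see a changed outcome. With 20 patients per arm, and the form of the dynamometry endpoint still open, that choice could end up being made after the data are seen.

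**Working it through.** The point rests on comparing passages; no figure in the plan depends on it.

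**1. Outcomes by section.**

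| Outcome | Section 2 (efficacy) | Section 4 (scheduled or recorded) | Section 12 (analysis) |
|---|---|---|---|
| Pain score | yes | yes | yes |
| Opioid consumption | yes | yes | yes |
| Quadriceps dynamometry | yes | yes, one time point (2 h) | no |
| Ambulation distance | yes | yes, two time points (POD0, POD1) | no |
| Hospital length of stay | no | yes | no |
| Tibial and common peroneal strength | no | no | yes |

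Counting ambulation and dynamometry separately, Section 2 names 4 efficacy measures. Section 12 covers 2 of the 4 and adds 1 that is in neither Section 2 nor Section 4.

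**2. Term search over the whole document.** Tibial and peroneal occur once each, both in the Section 12 sentence. Sciatic, ankle and flexion do not occur, so the assessment is not described under another name. Quadriceps, dynamometry and ambulation occur twice each, once in Section 2 and once in Section 4, and never in Section 12.

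**3. Could another measurement serve?** Section 4 has the surgeon determine the degree of knee extension before the operation. That is a preoperative observation. It is neither a strength test after the block nor a measure of either nerve.

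**4. Which nerve does the rationale concern?** Section 3 mentions motor effects three times. One is general, about avoiding motor block in chronic pain. The other two, quoted above, concern the femoral nerve. Quadriceps dynamometry fits that background; the only link from motor function to the tibial or common peroneal nerve is the Section 12 sentence itself.

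**5. What the general rule in Section 2 leaves open.** It supplies a test for dynamometry but not the quantity to be tested. Let B be the strength of the blocked leg and U that of the unblocked leg. Section 4 makes the measure leg-relative, which allows either D = B − U or R = B/U. Since D = U × (R − 1), two patients with the same ratio below 1 have different values of D whenever U differs. The two forms can therefore rank patients differently and give different test results.

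**6. Sample size.** With a difference of 2 and a standardised effect of 1.0, the implied SD is 2/1.0 = 2. At two-sided 0.05 and 80% power, the exact t-test solution is 16.71 per arm. Dividing by the minimum asymptotic relative efficiency of the Mann-Whitney test gives 16.71/0.864 = 19.3 (19.35 before rounding the input), hence 20 per arm and 40 in total, as planned. The calculation uses the pain score only, so nothing here alters it.

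**The case against.** The strongest reply is that this is a labelling slip. Section 12 does plan a between-group analysis of motor strength, the only scheduled strength measure is quadriceps dynamometry, and Section 2 supplies the test, sidedness and significance level. On that reading the outcome class and test family are present and only the nerve label is wrong. That may well be how the sentence arose, but nothing in the document says so, and the general rule cannot supply tibial or peroneal data.

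Four narrower objections have some force:

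- The protocol shows that no tibial or peroneal assessment is scheduled. That no such data will exist is an inference from this, though Section 4 offers no other source.
- Ambulation is named in Section 2, scheduled with units and days in Section 4, and covered by the general rule. On its own, its absence from Section 12 would be only missing detail. The same holds for length of stay.
- The motor-block sentence in Section 3 describes another technique, and the case series did report a gross observation. Section 3 supports the quadriceps reading but states no motor hypothesis for this trial. Sections 2 and 4 carry the point without it.
- The count of 4 efficacy measures becomes 3 if functional status is taken as one item. The contradiction does not depend on the count.

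None of these removes the conflict between Sections 4 and 12.

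**Conclusion.** The concern holds. The motor-strength analysis in Section 12 is wrong as written: it names an outcome with no scheduled measurement, while the strength outcome that Section 2 declares and Section 4 schedules is not named in the analysis section. One of the two additional secondary analyses in the sentence is affected, and the form of the dynamometry endpoint is undefined.

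The consequence is limited to secondary endpoints. This is a correction that should be made, and it does not threaten the main conclusion. The verdict assumes that Section 4 is the full schedule, which the cross-reference in Section 9 supports.

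**What to change.** In Section 12, replace the reference to the two nerves with quadriceps dynamometry 2 hours after the intervention, expressed relative to the unblocked leg as in Section 4 and compared between the SIFI and sham arms. State in advance whether the difference or the ratio is used. In the same place, list ambulation distance on POD0 and on POD1 as separate between-arm comparisons, with length of stay as a descriptive outcome. Say whether these secondary comparisons are adjusted for multiplicity or exploratory.

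The cost is essentially one sentence. The data are already planned, so no assessment is added and N does not change.

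If tibial and common peroneal testing is really intended, Sections 4 and 12 must be reconciled. Section 4 would then need the assessment added, with its method and timing, at greater cost. Dynamometry would still need its entry in Section 12.
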